5.1.3.3 Other imputations

Not applicable.

5.2 AEs coding/grading

Adverse events are coded using the Medical dictionary for regulatory activities (MedDRA) terminology. MedDRA version in effect prior to database lock will be used for CSR AE reporting.

AEs will be assessed according to the Common Terminology Criteria for Adverse Events (CTCAE) version 4.03.

5.3 Laboratory parameters derivations

CTC grading for blood differentials is based on absolute values. However, this data may not be reported as absolute counts but rather as percentage of WBC.

If laboratory values are provided as '<X' (i.e. below limit of detection) or '>X', prior to conversion of laboratory values to SI unit, these numeric values are set to X.

The following rules will be applied to derive the WBC differential counts when only percentages are available for a xxx differential

xxx count = (WBC count) * (xxx %value / 100)

Further derivation of laboratory parameters might be required for CTCAE grading. For instance, corrected calcium can be derived using the reported total calcium value and albumin at the same assessment using the following formula:

Corrected Calcium (mg/dL) = Calcium (mg/dL) - 0.8 [Albumin (g/dL)-4]

In order to apply the above formula, albumin values in g/L will be converted to g/dL by multiplying by 0.1), calcium values in mmol/L will be converted to mg/dL by dividing by 0.2495. For calculation of laboratory CTC grades 0 and 1, the normal range for derived corrected calcium is set to the same limits (in mg/dL) as for calcium.

CTC grades for the derived absolute WBC differential counts (neutrophils, lymphocytes) and corrected calcium will be assigned as described above for grading.

In order to derive the corresponding absolute normal range, the rule to be applied depends on the availability of the % range and the absolute range for the differential:

- If absolute range is NOT missing (% range is or is not missing), then use the absolute range provided by the site.
- If % range is NOT missing and absolute range is missing, then the % normal limits (i.e., LLN and ULN) are divided by 100 and multiplied by the corresponding normal limits of WBC count, e.g., for neutrophils (NEU):

LLN for NEU count = (LLN for WBC count) x (LLN for NEU%value / 100),

ULN for NEU count = (ULN for WBC count) x (ULN for NEU%value / 100)

5.4 Statistical models

5.4.1 Primary analysis

Not applicable.

5.4.2 Key secondary analysis

Not applicable.

5.5 Rule of exclusion criteria of analysis sets

All non-minor protocol deviations (any PD leading to exclusion from any analysis data set) are given in Table 5-4. The complete list of protocol deviations is given in VAP module 3 (Protocol Deviations).

Deviation code	Text description	Severity code
102	Unconfirmed diagnosis of PMF, PPV-MF or PET-MF	0
103	Patient without a palpable spleen >= 5 cm	1
104	Patient without 2 or more risk factors	1
110	Patient had previous therapy with a JAK2 inhibitor	1
E07	Patient had splenic irradiation within 12 months prior to screening	1
E09	Patient being treated with another investigational drug not intended for MF or having been treated with such a drug within 14 days prior to Baseline or 6-half lives of the drug, whichever is longer	1
E16	Patient is unable to comprehend or is unwilling to sign the ICF	8
C01	Patient with no post-baseline safety assessments	5
C02	Patient with no post-baseline spleen volume assessment	1
M03	Use of any investigational medication other than INC424 during the study	2
M04	Use of any other drugs for MF including hydroxyurea, interferon, thalidomide, busulfan, lenalidomide or anagrelide during the study	2
M05	Use of potent CYP3A4 inducers	20

Table 5-4Major protocol deviations

Table 5-5 shows the subject classification based on the severity code for each analysis population.

Table 5-5	S	ubject o	classifi	cation		
	Severity code					
Population	0	1	2	5	8	20
FAS	No	Yes	Yes*	Yes	No	Yes
PPS	No	No	Yes*	Yes	No	Yes
SAF	Yes	Yes	Yes*	No	No	Yes
PAS	No	Yes	Yes*	Yes	No	No

Note: 'Yes' means inclusion in the analysis set, 'No' means exclusion from the analysis set.

* means that partial data post-deviated date will NOT be used for any analyses.

6 Reference

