2.1 Data analysis general information

The final CSR analysis will be performed by Novartis. SAS® version 9.4 (or later version if available at time of database lock) will be used to perform all data analyses and to generate tables, figures and listings.

Unless otherwise specified, categorical data will be summarized by frequency count and percentages. Percentages will be calculated using the number of subjects in the relevant population or subgroup as the denominator.

The final analysis will be performed after final Data Base Lock (DBL).

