2.1.1 General definitions

Study drug and study treatment

Both study drug and study treatment refer to INC424.

Date of first administration of study drug

The date of first administration of study drug is defined as the first date when a nonzero dose of study drug is administered and recorded on the dose administration record (DAR) page of the electronic case report form (eCRF).

Date of last administration of study drug

The date of last administration of study drug is defined as the last date when a nonzero dose of study drug is administered and recorded on DAR page of the eCRF.

Study day

Study day 1 is the date of first administration of study drug.

The study day for all assessments will be calculated as follows:

1. If date of assessment occurred on or after the start of study treatment, then

Study day = Date of assessment - Start date of study treatment + 1.

2. If date of assessment occurred before the start of study treatment, then

Study day = Date of assessment - Start date of study treatment.

The study day will be displayed in the data listings.

Baseline

Unless otherwise specified, the baseline measurement for any parameter is defined as the last non-missing pre-dose value (scheduled or unscheduled) before the first administration of study drug.

On-treatment assessment/event

On-treatment period is from day of first dose of study drug to 30 days after last dose of INC424.

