2.8 Safety analyses

For all safety analyses, the safety set will be used.

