2.8.1 Adverse events (AEs)

In this study, an adverse event is defined as the appearance of (or worsening of any preexisting) undesirable sign(s), symptom(s), or medical condition(s) that occur after a patient's signed Informed Consent has been obtained. With exception of screening failure patients, adverse events that begin or worsen after Informed Consent will be recorded in the Adverse Events eCRF. Summary tables for adverse events have to include only adverse events that started or worsened during the on-treatment period, the treatment-emergent adverse events. Listings will include all reported AEs in the database (except AEs that started after the study completion date) and such AEs that have an onset prior to Study Day 1 are to be flagged in the listing.

Both system organ class (SOC) and preferred term (PT) as listed by the Medical Dictionary for Regulatory Activities (MedDRA, the latest version) will be used for all AE summaries. The following summaries will be produced:

- Overall summary of adverse events
- Adverse events, regardless of study drug relationship, by primary system organ class
- Adverse events, regardless of study drug relationship, by preferred term
- Adverse events, regardless of study drug relationship, by primary system organ class and preferred term
- Adverse events, regardless of study drug relationship, by study period, primary system organ class and preferred term
- Adverse events suspected to be related to study drug, by preferred term
- Adverse events suspected to be related to study drug, by primary system organ class and preferred term
- Serious adverse events, regardless of study drug relationship, by primary system organ class and preferred term
- Adverse events leading to discontinuation, regardless of study drug relationship, by preferred term
- Adverse events leading to discontinuation, regardless of study drug relationship, by primary system organ class and preferred term
- Adverse events leading to dose adjustment or study drug interruption, regardless of study drug relationship, by preferred term
- Adverse events leading to dose adjustment or study drug interruption, regardless of study drug relationship, by primary system organ class and preferred term

Clinical trial safety disclosure

For the legal requirements of ClinicalTrials.gov, the following summaries will be produced:

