- On-treatment AEs (i.e., treatment-emergent AEs) which are not serious AEs with an incidence greater than 5% and on on-treatment serious AEs by primary system organ class and preferred term
- Serious AEs suspected to be related to study treatment by primary system organ class and preferred term

If for a same patient, several consecutive AEs (irrespective of study treatment causality, seriousness and severity) occurred with the same system organ class and preferred term:

- a single occurrence will be counted if there is ≤ 1 day gap between the end date of the preceding AE and the start date of the consecutive AE
- more than one occurrence will be counted if there is > 1 day gap between the end date of the preceding AE and the start date of the consecutive AE

For occurrence, the presence of at least one serious AE / serious AE suspected to be related to study treatment / non-serious AE has to be checked in a block e.g., among AE's in a ≤ 1 day gap block, if at least one serious AE is occurring, then one occurrence is calculated for that serious AE.

The number of deaths resulting from serious AEs suspected to be related to study treatment and serious AEs irrespective of study treatment relationship will be provided by primary system organ class and preferred term.

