2.8.3 Laboratory data

Clinical laboratory tests including hematology, clinical chemistry, urinalysis, lipid panel, coagulation test, and immunology will be done for each patient during the study in accordance with the 'Visit Evaluation Schedule' described in the protocol. If specific safety issue arise, additional, unscheduled laboratory tests/analyses may be done at the discretion of the investigators. A central laboratory will be used for analysis of all specimens collected except for hematology, pregnancy tests, other urine analysis and serology for hepatitis virus and HIV which will be performed locally.

Laboratory data reported will be graded by programming based on the Common Terminology Criteria for Adverse Events (CTCAE) Version 4.0.3, where applicable. A severity grade of 0 will be assigned when the value is within normal limits. (In the case when a laboratory normal range overlaps into the higher (i.e., non-zero) CTC grade, the laboratory value will still be taken as within normal limits and assigned a CTC grade of zero.) Some parameters may be converted in Standard International (SI) units if laboratory measurement with any other unit was reported. For the summarization of laboratory measurements and listing of laboratory measurements, SI unit will be used as default with original or converted measurements. For laboratory tests where grades are not defined by CTCAE, results will be graded by the low/normal/high classifications based on laboratory normal ranges.

The following summary will be produced for laboratory parameters in hematology:

• Shift tables using CTC grades to compare baseline to the worst on-treatment value

All laboratory data will be listed with updated data for the final analysis. Patient with abnormal hematology values will be also listed.

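### SAP Table 5-5 keeps patients with deviations M03 or M04 in the Safety Set but discards their later data, so crude safety incidences can only be understated

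*SAP*

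**What the plan says.** Table 5-4 in SAP section 5.5 gives severity code 2 to two deviations: M03, use of another investigational drug, and M04, "Use of any other drugs for MF including hydroxyurea, interferon, thalidomide, busulfan, lenalidomide or anagrelide during the study". Table 5-5 enters code 2 as an asterisked Yes in all four rows, including the Safety Set (SAF). Yes keeps the patient in the set. The footnote to the asterisk "means that partial data post-deviated date will NOT be used for any analyses".

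The other safety rules contain no cut at a deviation:

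- SAP 2.8: "For all safety analyses, the safety set will be used". Protocol 10.1.2 says the same.
- SAP 2.1: "Percentages will be calculated using the number of subjects in the relevant population or subgroup as the denominator".
- SAP 2.1.1: "On-treatment period is from day of first dose of study drug to 30 days after last dose of INC424". Protocol 10.5.5.1 has the same window.
- SAP 2.8.1: "Summary tables for adverse events have to include only adverse events that started or worsened during the on-treatment period".

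SAP section 4 declares no change from the analyses specified in the protocol.

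**The concern.** The two sets of rules cannot both be followed. A programmer who applies Table 5-5 drops the adverse events, serious adverse events (SAEs), deaths and laboratory values that fall after the deviation but inside the on-treatment window. The patient still counts in the denominator. A programmer who applies SAP 2.1.1 and 2.8.1 keeps them.

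Safety is a secondary objective and makes up most of the final study report. The footnote reaches the adverse event summaries, the display of on-treatment deaths, the hematology tables described as "Shift tables using CTC grades to compare baseline to the worst on-treatment value" and the public disclosure table for "On-treatment AEs (i.e., treatment-emergent AEs) which are not serious AEs with an incidence greater than 5" per cent. A patient who adds a second drug while taking INC424 is also one whose later toxicity a reader would want to see counted.

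**Working it through.** **Is the asterisk a slip that was meant only for efficacy?** Table 5-5 does not support that reading. The SAF row was set separately from the Full Analysis Set row: code 0 is Yes for SAF and No for FAS, and code 5 (no post-baseline safety assessment) is No for SAF and Yes for FAS. The asterisk appears in the SAF row, and the footnote covers all analyses.

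**Direction.** The denominator is fixed by SAP 2.1 and the truncation only removes events. A crude patient incidence can therefore stay the same or fall. Likewise, a worst on-treatment grade can only stay the same or look milder.

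**Bound.** Let k be the number of M03/M04 patients and N the size of the Safety Set. Each affected patient can be lost at most once from a given row, so the understatement is at most k/N. SAP section 1 gives 120 patients, and N = 120 is assumed for the Safety Set. One patient is 1/120 = 0.83 points. For k = 6, 12 and 18 the bound is 5.0, 10.0 and 15.0 points.

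**Disclosure threshold.** The cut-off is strictly above 5%. With N = 120, 7/120 = 5.83% qualifies and 6/120 = 5.00% does not. A term seen in 7 patients drops out if one of them is lost.

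**Illustration for patients with any SAE.** None of these inputs is in the documents. Assume a first-SAE rate L = 0.3 per year, a horizon T = 3 years (incidence 1 − exp(−0.9) = 59%), a deviation time D uniform on (0, T), and a window w = 30 days = 0.082 years. After the deviation the rate is multiplied by r = 1 to 3. A patient is lost if there is no SAE before D and at least one after D inside the window.

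- Mean of exp(−L·D) = (1 − exp(−0.9))/0.9 = 0.659.
- *INC424 stops at the deviation.* The loss per affected patient is 0.659 × (1 − exp(−r·L·w)), which is 0.016 for r = 1 and 0.047 for r = 3.
- *INC424 continues to year 3 (upper bound).* The loss is the mean of exp(−L·D) × (1 − exp(−r·L·(T + w − D))), which is 0.263 for r = 1 and 0.484 for r = 3.

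Multiplying by k/120 gives the understatement in percentage points:

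| Path | r | k = 6 | k = 12 | k = 18 |
|---|---|---|---|---|
| Stops | 1 | 0.08 | 0.16 | 0.24 |
| Stops | 3 | 0.23 | 0.47 | 0.70 |
| Continues | 1 | 1.31 | 2.63 | 3.94 |
| Continues | 3 | 2.42 | 4.84 | 7.26 |

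On the stopping path, the chance that at least one SAE patient is lost is 1 − (1 − 0.016)^6 = 9% for k = 6, r = 1, and 1 − (1 − 0.047)^18 = 58% for k = 18, r = 3.

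**Simpler check.** Let a row have true incidence p, and let a share f of the affected patients with that event have it only after the deviation. The shortfall is p·k·f/120. For p = 45%, k = 6 and f = 0.5 it is 0.45 × 6 × 0.5/120 = 1.1 points. Over k = 1 to 12, f = 0.25 to 1 and p = 20% or 45%, it runs from 0.04 to 4.5 points. These inputs are also assumptions.

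**The case against.** The strongest objection is that the effect may be negligible. Protocol 6.3.3 prohibits these drugs, and protocol 7.1.4.1 lists new cancer therapy and non-compliance among the reasons for ending treatment. A patient who stops INC424 at the deviation loses only about 30 days of on-treatment data. Protocol 7.1.5 also allows an earlier follow-up visit once new therapy begins. All of this stands as a limit on size, and the larger figures above apply only to patients who stay on INC424. It does not remove the contradiction: protocol 7.1.4.1 still follows all patients for 30 days, and an earlier visit does not discard data already collected.

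A second objection is that later events may be due to the added drug, so a cut isolates INC424. That would justify a labelled sensitivity analysis. It does not justify an undeclared cut against the SAP's own on-treatment window.

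Third, the listings stay complete: all adverse events, deaths, laboratory values, ECGs and vital signs are listed. That is correct, but a listing does not correct a summary percentage or a disclosure table.

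Fourth, the plan for the Week 24 report is a separate document not available here. If it used the same cut, changing only the final report would affect comparability. That is a reason to state the rule openly.

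**Conclusion.** The concern holds. Table 5-5, as written, contradicts SAP 2.1.1 and 2.8.1 and protocol 10.5.5.1, and SAP section 4 does not declare the departure. Following it can only lower crude safety incidences.

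The amount cannot be computed, because the documents give neither the number of M03/M04 patients nor the timing of their deviations. It may be zero. If the Safety Set has 120 patients, the limit is 0.83 points per affected patient. Under the assumed SAE rates and 6 to 18 affected patients, the understatement is 0.08 to 0.70 points if INC424 stops at the deviation and 1.3 to 7.3 points if it continues to year 3. This should be fixed, although there is no evidence that any safety conclusion would change.

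A smaller point is that the same asterisk applies to efficacy. It does not match the best response definition or the duration-of-response rules in SAP 2.7. No effect size is claimed there.

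**What to change.** - Remove the asterisk from the SAF row of Table 5-5, so that every event in the on-treatment window is counted.
- Report the number of M03/M04 patients and how many of them stayed on INC424 after the deviation.
- If a view that excludes data after other therapy is wanted, show it as a labelled sensitivity analysis beside the full summary. If the Week 24 report used the cut, say so in the final report.
- In SAP 2.7, add one sentence saying whether Table 5-5 or the section's own rules govern best response rate and duration of response. Show the other as a sensitivity analysis, and record any departure from protocol 10.5.3 and 10.5.4 in SAP section 4.

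The cost is one table edit, a sentence or two and a rerun of existing programs. Some safety counts may rise slightly.
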